### Sustained Disability Progression

Sustained disability progression is defined as at least a 1.0 point increase on the EDSS score from Baseline, confirmed after a 3 month and a 6 month period. Confirmation of MS disease progression must not occur at the time of a relapse. If the patient is scheduled to be evaluated to confirm disability at the time of a relapse, the disability event must be assessed at a later visit, which may be the next scheduled visit, or at an unscheduled visit conducted after the relapse has resolved. The date of the initial visit at which the minimum increase in the EDSS is met will be the date of onset of the progression (tentative progression).

Disability progression can be confirmed at the early withdrawal visit, according to the rules above, as long as the early withdrawal visit is not also a relapse assessment visit.

Death due to MS will be counted as a confirmed progression. If the patient was in the midst of a tentative progression at the time of death, the progression date will be the date of the start of the progression. Otherwise, the progression date will be the date of death.

#### Time to Censor

A patient will be censored if follow-up ends before a sustained progression occurs, whether due to the patient completing study, withdrawing from the study, or due to the cutoff of data collection for the analysis. The censor date will be the date of the last EDSS assessment or date of last dose of study drug, whichever is later. This will apply to both 3-month confirmations and 6-month confirmations of progression. As such, a patient who is confirmed as having a progression after 3 months but does not have a 6-month confirmation will be considered as having an event in the 3-month analysis but will be censored in the 6-month analysis.

Patients in the ITT population who withdraw from the study after the Baseline visit but prior to the first clinical evaluation scheduled visit will be censored at Baseline.

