# Part B

Part B is a randomized, double-blind, double-dummy comparison of RPC1063 to IFN  $\beta$ -1a in patients with RMS, per revised 2010 McDonald criteria (McDonald, 2010; Polman, 2011). Part B will commence after the DMC reviews the Part A interim analysis data and performs a thorough safety review. Patients dosed in Part A will be ineligible for participation in Part B.

Approximately 1200 patients who meet eligibility criteria as assessed during the 30-day screening period will be randomly assigned 1:1:1 to receive one of the three following regimens for 24 months:

- IFN β-1a 30 µg intramuscular (IM) weekly
- 0.5 mg RPC1063 oral capsule daily
- 1 mg RPC1063 oral capsule daily

The randomization will be stratified by baseline EDSS ( $\leq 3.5, > 3.5$ ) and country.

A "dual assessor" approach will be used to evaluate efficacy and safety to prevent potential unblinding as result of observed efficacy, AEs, or laboratory changes (refer to Section 9.1.2.1 for additional details). The treating investigator will evaluate patients every 3 months throughout the study and, if necessary, at unscheduled visits for relapses occurring between scheduled visits.

[figure not shown]
The blinded evaluator will assess the EDSS. Blinded study coordinators or EDSS evaluators will perform the MSFC and LCLA assessments. The Cognitive Function subscale of the

MSQOL-54 will also be assessed to evaluate subjective cognitive impairment. The Paced Auditory Serial Addition Test (PASAT-3) of the MSFC will also be used to evaluate cognitive function.

All efforts will be made to follow patients who discontinue from the treatment due to lack of response, AEs, or other reasons, even if alternative treatment is given. These patients will be followed for collection of safety data, including lymphocyte recovery, and for the assessment of their disease status.

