- 1 The Unscheduled Relapse Assessment Visit will be conducted in the case of a suspected relapse (see Section 9.1.2.3). After the Unscheduled Relapse Assessment Visit, patients should return to their usual visit schedule.
- 2 Patients who prematurely discontinue study treatment will be asked to complete an Early Termination visit.
- 3 Laboratory tests include Hematology, Chemistry, and Urinalysis.
- 4 Urine beta-hCG. If the urine pregnancy test is positive, do not dose and confirm with a serum pregnancy test.
- 5 Brain MRI scans will include a T2 and T1 scan (with and without Gadolinium).
- 6 Pulmonary function tests will include FEV1 and FVC measurements, and DLCO. If any abnormalities occur, they will be followed until such time as resolution is confirmed or no further improvement is expected by the investigator (based on a follow-up period of not less than 3 months).
- 7 If abnormal OCT findings, or visual signs or symptoms of macular edema are observed, a general ophthalmologic examination including eye history, visual acuity, and dilated ophthalmoscopy will also be performed.

Table 5 Cardiac Monitoring During Dose Titration – Days 1, 5, and 8

	Cardiac Monitoring								
	Day 1/Part A Day 169 (W24)			Day 5 				Day 8 	
	Predose	Hourly for 6	At Hour 6	Continuous	Predose	Hourly for	At Hour 6	Continuous	Continuous
		hours		Monitoring		6 hours		Monitoring	Monitoring for 24
				for 24 hours				for 24 hours	hours
Procedure							<	/	
Vital signs	X	X			X	X			
12-lead ECG	$X^2$		X		$X^2$		X		
Holter monitoring 				$X^4$				X	X
Assess Discharge			X 			,	$X^{6,7}$		
Criteria 			Λ			7.	A c ,		

ECG = electrocardiogram

- 1 Day 5 and Day 8 procedures will be conducted in the first 75 patients
- 2 Baseline or predose ECG should be provided by the site and be available for comparison to the postdose ECG in order to determine if discharge criteria are met
- 3Begin 15 minutes predose and continue for 24 hours after dose.
- 4 Holter monitoring will be performed on Day 1 for Part A patients only, and will not be performed in Part B or on the Week 24 (Day 169) visit for Part A.

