# 10.5. Early Termination Visit

Patients who prematurely discontinue study treatment will be asked to complete an early termination visit. The following assessments will be performed:

- Blood/urine sampling for the following laboratory tests:
  - Hematology: RBC count, total and differential WBC count (basophils, eosinophils, lymphocytes, monocytes, and neutrophils), platelet count, hemoglobin, hematocrit, MCV, MCH, and MCHC
     Note: All total WBC and differential WBC counts will be blinded during the study.
  - Blood chemistry: sodium, potassium, chloride, calcium, magnesium, phosphate, blood urea nitrogen, random glucose, albumin, alkaline phosphatase, creatinine, SGPT/ALT, SGOT/AST, GGT, amylase, total bilirubin, conjugated bilirubin, hemoglobin A1c. Abnormal laboratory parameters inconsistent with clinical presentation of MS or suspicious of underlying medical condition should be repeated for accuracy. If an increase of amylase above the clinically notable value (≥ 300 U/L) is observed at any post randomization visit, lipase should be tested to determine the origin of elevated amylase (pancreatic versus extra pancreatic)
  - Urinalysis: leukocytes, specific gravity, bilirubin, blood, glucose, ketones, pH, protein, and urobilinogen
  - Urine beta-hCG (females of childbearing potential only). If the urine pregnancy test is positive, do not dose and confirm with a serum pregnancy test.
  - Coagulation panel: PT and partial thromboplastin time PTT
  - sTSH

- PK sampling
- Complete physical examination: including evaluation of heart, lung, head and neck, abdominal, neurological, skin, and extremities
- Weight
- Vital signs: body temperature, blood pressure and heart rate
- 12-lead ECG
- Review study drug accountability and compliance
- Brain MRI
- EDSS and neurological examination
- MSFC and LCLA
- MSQOL-54
- Pulmonary function tests including FEV1, FVC, and DLCO measurements
- OCT evaluation
- Dermatological examination
- Suicidality assessment using the C-SSRS
- Record concomitant therapy
- Record AEs/SAEs

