### 8.2.1. Extent of Exposure

Extent of exposure is defined as the total number of days a patient is exposed to any study drug. Because there is no medication diary, the extent of exposure is defined as the total number of days from the first dose date (Day 1) to the last dose date as recorded on the End of Study/Early Withdrawal page on the CRF. If the last dose date on the End of Study/Early Withdrawal page is missing or a patient is lost to follow-up, but the drug accountability log confirms that the patient has taken study drug, the visit date following the last completed drug accountability log will be used.

The extent of exposure and study drug exposure will be summarized in a table by summary statistics for the Safety Population.

The listing will present patient data for the first dose date, last dose date, extent of exposure, and study drug exposure.

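### Disability progression is censored at the later of last EDSS and last dose, so patients without a final EDSS stay at risk when progression can no longer be recorded; the bias is small and easily removed

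*SAP*

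**What the plan says.** The general rule in SAP 9.2.1, Time to Censor, is: "The censor date will be the date of the last EDSS assessment or date of last dose of study drug, whichever is later". It applies to both the 3-month and the 6-month confirmed analyses. The next paragraph makes an exception: patients in the ITT population who withdraw "prior to the first clinical evaluation scheduled visit will be censored at Baseline".

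Other provisions bear on how often last dose can fall after last EDSS:

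- Protocol 9.1, Part B: "The treating investigator will evaluate patients every 3 months throughout the study". Table 3 schedules an EDSS at each visit from Month 3 to Month 24.
- Protocol Table 4, footnote 2: "Patients who prematurely discontinue study treatment will be asked to complete an Early Termination visit". Protocol 10.5 lists "EDSS and neurological examination" among that visit's procedures.
- SAP 9.2.1, Sustained Disability Progression: "Disability progression can be confirmed at the early withdrawal visit, according to the rules above", unless that visit is also a relapse assessment. The same section adds: "Death due to MS will be counted as a confirmed progression".
- SAP 8.2.1 (Extent of Exposure) covers a missing last-dose date or loss to follow-up. If the accountability log confirms dosing, "the visit date following the last completed drug accountability log will be used". Time to Censor does not refer to this rule.

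**The concern.** The SAP dates onset at the visit where the EDSS increase is first met. Apart from death due to MS, no event can therefore be recorded after a patient's last EDSS. Days between last EDSS and a later last dose add to the risk set but cannot produce an EDSS event. If one arm has more such patients, its hazard is diluted more and the hazard ratio moves in that arm's favour.

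The endpoint is third in the rank-ordered key secondary sequence (SAP section 5), so it is part of the type 1 error plan, and its data are also to be pooled with RPC01-301. None of the four planned sensitivity analyses censors at last EDSS. Two treat early leaving as progression, which answers a different question.

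**Working it through.** **No figure to reproduce.** Neither document gives an event count, power or hazard ratio for disability progression. Dropout is given only overall: 17% in the protocol and about 12% in the SAP. Dropout by arm, the progression rate and the share of dropouts without a final EDSS are assumptions below.

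**When a gap can arise.**

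| Situation | Last EDSS against last dose | Effect of the rule |
|---|---|---|
| Stops treatment, attends Early Termination visit | normally at or after last dose | none |
| Withdraws before first scheduled evaluation | exception: censored at Baseline | none |
| Leaves later, no final EDSS | last dose may be later by up to about one visit interval (91 days, ±5-day windows) | unassessed time added |
| As above, last dose moved to the next visit date | about 91 days later | more unassessed time added |

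**Person-time approximation.** For the arm with more dropout against the other,

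factor on the hazard ratio = 1 / (1 + Δ × g / T),

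where Δ is the difference between arms in dropout without a final EDSS, g the mean gap and T the mean follow-up. T is assumed to be 656 days, which is what 20% dropout spread evenly over the 729-day schedule gives: 729 × (1 − 0.20/2) = 656. With Δ = 0.10:

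- g = 45.5 days (last dose midway between visits on average): 0.10 × 45.5/656 = 0.0069, factor 0.993.
- g = 91 days (last dose at the next visit date): 0.10 × 91/656 = 0.0139, factor 0.986.
- g = 182 days: 0.10 × 182/656 = 0.0277, factor 0.973.

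**Simulation, no true effect.** There were 40,000 patients per arm, EDSS at the eight scheduled visits, confirmation at 76 days or more, uniform dropout times and the Baseline exception kept. A quarter of onsets were dated at unscheduled visits. Both censoring rules were applied to the same data. Entries are the hazard ratio under the SAP rule divided by that under last-EDSS censoring, for the arm with more dropout. Assumed progression of 8% or 15% made almost no difference.

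| Case | 20% vs 10% dropout | 30% vs 10% dropout |
|---|---|---|
| A quarter of dropouts lack a final EDSS | 0.998 | 0.997 |
| All lack one | 0.993 | 0.985 |
| All lack one, last dose at next visit | 0.986 | 0.972 |
| All lack one, mean gap about 200 days (extreme) | 0.97 | 0.94 |

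**Simulation, true hazard ratio 0.75.** With 15% progression, 150,000 per arm and no final EDSS for any dropout:

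- 17% dropout in both arms: about 0%.
- IFN β-1a 22%, RPC1063 12%: about +0.6 to +0.7%; about +1.4 to +1.5% with last dose at the next visit.
- Dropout reversed: the same sizes with a negative sign.
- Half the dropouts have an Early Termination EDSS: about 0.3 to 0.4%, or 0.7 to 0.8% with last dose at the next visit.

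On a hazard ratio of 0.75, a 1.5% shift gives 0.75 × 1.015 = 0.761 or 0.75 × 0.985 = 0.739.

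**Against sampling error.** Take 15% as the comparator rate. Then 400 patients give about 60 events, and roughly 60 × 0.75 = 45 in an RPC1063 arm. The standard error of the log hazard ratio is about √(1/60 + 1/45) = 0.197. A 1.5% shift is ln(1.015) = 0.0149, and 0.0149/0.197 = 0.08 standard errors.

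**The case against.** The strongest reply is that the protocol largely closes the gap. Patients who stop treatment are asked to attend a visit with an EDSS, and progression can be confirmed there. Early leavers are censored at Baseline, and scheduled EDSS visits are three months apart. MS death still counts as an event inside a gap. All of this stands. It limits the size of the bias but does not remove it, because an Early Termination visit is requested and cannot be guaranteed, least of all in patients lost to follow-up.

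Three stronger readings are tempting, and the documents do not support them.

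- A reader might infer that the SAP places lost patients in the next visit's risk set. SAP 8.2.1 defines exposure and is not cited in Time to Censor. If the visit it refers to was attended, Table 3 provides an EDSS there from Month 3 onward and no gap arises. The 1.5% figure applies only if the rule is borrowed and the visit was not attended.
- A reader might see a contradiction between the general rule and the Baseline rule. The second is a specific exception and governs its own case. It follows the principle that unassessed time is not time at risk, which the general rule does not follow.
- A reader might infer that dropout as such biases the result, or that the rule favours RPC1063. The trigger is dropout without a final EDSS, and neither document splits dropout by arm. If IFN β-1a loses more such patients, the bias runs against RPC1063.

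It is also fair to say that last-EDSS censoring leaves a blind period. An onset first seen within 76 or 166 days of the last EDSS cannot be confirmed under either rule. For a 10-point dropout difference that is 0.10 × 76/656 = 1.2% or 0.10 × 166/656 = 2.5% of person-time, comparable with or larger than the effect at issue.

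**Conclusion.** The point holds as a minor one. The rule keeps some patients in the risk set when only MS death could be recorded, and it lowers the apparent hazard in the arm with more of them. With dropout differing by 10 points and no final EDSS for any dropout, the shift is about 0.6 to 0.7% of the hazard ratio, or about 1.5% if last dose is also moved to the next visit date. It is roughly half that if half the dropouts have an Early Termination EDSS, and about nil if dropout is equal. A distortion of several percent would need a much larger imbalance or gaps of around 200 days; ordinarily a dropout adds at most about one visit interval out of eight. These sizes rest on the assumed progression rate, dropout by arm and share without a final EDSS. The direction in this trial cannot be known from the documents, and the effect would not by itself be expected to change a conclusion.

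**What to change.** In SAP 9.2.1, Time to Censor, set the censor date to the date of the last EDSS assessment, or Day 1 if there is none after baseline. Keep death due to MS as an event, dated as now. This gives one rule for all patients and makes the separate Baseline exception unnecessary.

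Keep the later of last EDSS and last dose as a sensitivity analysis, and state there whether the substituted date in SAP 8.2.1 applies. Report by arm how many patients have a last dose after their last EDSS, and the length of the gap. Use the same rule in the pooling plan with RPC01-301.

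The cost is one sentence in the SAP before database lock, one extra model run and a short table. No new data are needed. The change does not address the 76- or 166-day confirmation window, which is a separate matter.

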#### Analysis Method

All disability progressions will be identified as confirmed after 3 months, confirmed after 6 months, or unconfirmed prior to database lock. The primary analysis of time to disability progression will be analyzed by a Cox proportional hazards model with factors

for treatment group, adjusted for region, age at Baseline and Baseline EDSS score. Handling of ties will be according to Efron. The hazard ratio, associated 95% CI, and p-values will be reported.

A Kaplan-Meier analysis on the difference in time to disability progression curves will also be performed. The estimated median time to disability progression will be reported, along with the associated 95% CI and log-rank p-values. A Kaplan-Meier plot will also be produced.

Each of these analyses will be performed on disability progressions confirmed after 3 months and again on disability progressions confirmed after 6 months.

Sensitivity analyses will be performed and include the following:

- Counting patients with a Baseline EDSS = 0 as a progression only if the EDSS score increases by at least 1.5 points
- Including unconfirmed progressions in each analysis
- Counting premature study discontinuations as confirmed progressions in each analysis
- Including unconfirmed progressions and counting premature discontinuations as progressions in each analysis

All disability progressions will be listed.

## 9.3. Other Secondary Efficacy Endpoints

The other secondary endpoints are:

- Proportion of patients who are GdE lesion-free at Month 24
- Proportion of patients who are new or enlarging T2 lesion-free at Month 24
- Percent change in normalized brain volume (atrophy) on MRI scans from Baseline to Month 24
- Change in MSFC score from Baseline to Month 24 (including the low-contrast letter acuity test [LCLA] measurement of visual function as a component)
- Change in MSQOL-54 score from Baseline to Month 24

### 9.3.1. Analysis

Secondary Endpoints: The proportion of patients who are GdE lesion-free at Month 24, and the proportion of patients who are T2 lesion-free at Month 24

Each of these endpoints will be analyzed using a Cochran-Mantel-Haenszel (CMH) test

stratified by region and EDSS category at Baseline. The numbers and percentages of patients with 0, 1-2, 3-4, and  $\geq$  5 lesions will be reported. The proportion of patients who are lesion-free will be reported along with the associated 95% CI. The difference in proportions between each RPC1063 group and the IFN  $\beta$ -1a group will also be reported with the associated 95% CI and CMH p-value. Patients who are missing the Month 24 MRI data will be considered non-responders, i.e., as not being lesion-free.

Sensitivity analyses will be conducted using the LOCF method for replacing missing Month 24 MRI data and on the subset of patients with non-missing Month 24 MRI data (observed cases analysis).

Secondary Endpoint: Change in normalized brain volume (atrophy) on MRI scans from Baseline to Month 24

Brain volumes will be reported in cm^3. If the data are collected in mm^3, then a transformation will be applied by dividing the result in mm^3 by 1000 to convert to cm^3 prior to analysis.

Actual brain volumes, change from Baseline to each visit, and percent change from Baseline to each visit will be summarized. Comparisons of the change and percent changes between the treatment groups will be analyzed using an analysis of covariance (ANCOVA) model adjusted for region, EDSS category at Baseline, and brain volume at Baseline. The mean difference between each RPC1063 treatment group and IFN  $\beta$ -1a will be reported with the associated 95% CI and p-value. Patients with missing data will have their results imputed via LOCF.

Secondary Endpoint: Change in MSFC score from Baseline to Month 24 (including the low-contrast letter acuity test [LCLA] measurement of visual function as a component)

The MSFC score is a battery of the following 3 individual scales:

- The Timed 25-Foot Walk is a quantitative measure of lower extremity function
- The 9-Hole Peg Test is a quantitative measure of upper extremity (arm and hand) function
- The Symbol Digit Modalities Test (SDMT) is a measure of cognitive impairment that assesses attention, visuoperceptual processing, working memory, and psychomotor speed

The MSFC z-score is calculated by creating z-scores for each component of the MSFC, as explained below, and averaging them to create an overall composite score, i.e.,

MSFC z-score = 
$$(Z_{25\text{-foot-walk}} + Z_{9HPT} + Z_{SDMT})/3$$
, and

MSFC z-score (LCLA) =  $(Z_{25\text{-foot-walk}} + Z_{9\text{HPT}} + Z_{SDMT} + Z_{LCLA})/4$ , where  $Z_{xxx}$  refers to Z-scores

A z-score represents the number of standard deviations a patient's test result is higher (z > 0) or lower (z < 0) than the average test result (z = 0) of the reference population.

The following describes the scoring, and rules for missing value imputation for each component.

Timed 25-Foot Walk Z-score Calculation

The Z-score is calculated as in the following formula:

$$Z_{25\text{-foot-walk}} = (-1) * \frac{((t_1 + t_2)/2) - MEAN(reference)}{SD(reference)}$$

where  $t_1$  and  $t_2$  are the time (in seconds) from the two trials, and the mean (reference) and SD (reference) are the mean and standard deviation respectively, of baseline values for the reference population. The reference population will be the study population.

For missing post-Baseline values, if a patient is missing only one trial for any post-Baseline visit, then the score from the non-missing trial will be used to calculate the Z-score. The steps outlined above will remain the same except the actual times will not be averaged.

The missing data algorithm suggested by the MSFC manual will be used to impute missing values. If both scores from the two trials are missing for any post-Baseline visit, due to MS related physical limitation or other physical limitations, then the patient will be given a Z-score of -13.7 for the Timed 25-Foot walk. If the reasons for missing scores on both trials are due to other reasons (non-compliance, missed visits), then LOCF from post-Baseline values will also be used as to impute the z-score for that visit. If a value is not available to carry forward, the mean of the available z-scores using all available data from the same treatment group, will be calculated at the specified visit and used as the imputed value. Values imputed using the mean will not be carried forward to other visits.

If a patient has missing data at Baseline for either trial, then the mean of the available z-scores will be evaluated by treatment group and used as the imputed value.

9HPT Z-score Calculation

Z-score for the 9HPT is calculated as in the following formula:

$$Z_{9HPT} = \frac{((\frac{1}{(t_{11} + t_{12})/2} + \frac{1}{(t_{21} + t_{22})/2})/2) - MEAN(reference)}{SD(reference)}$$

where  $t_{11}$ ,  $t_{12}$ ,  $t_{21}$ ,  $t_{22}$  are the time (in seconds) taken to complete for dominant hand trial 1, dominant hand trial 2, non-dominant hand trial 1, and non-dominant hand trial 2, respectively. The mean (reference) and SD (reference) are the mean and standard deviation, respectively, of reference population's baseline score. The reference

population will be the study population.

For missing post-Baseline values, if any of the times from the two trials of the same hand is missing, then the score from the non-missing time will be used to calculate the Z-score. The steps outlined above will remain the same except the actual times will not be averaged.

The missing data algorithm suggested by the MSFC manual will be used to impute missing values. If both scores from either hands are missing for any post-Baseline visit, due to MS related physical limitation or other physical limitations, then the patient will be given a Z-score will be calculated using a value of 777 seconds. If the reasons for missing scores on both trials are due to other reasons (non-compliance, missed visits), then LOCF from post-Baseline values will also be used as to impute the z-score for that visit. If a value is not available to carry forward, the mean of the available z-scores using all available data from the same treatment group, will be calculated at the specified visit and used as the imputed value. Values imputed using the mean will not be carried forward to other visits.

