The key secondary endpoints of cumulative number of new or enlarging T2 lesions between baseline and Month 12 and the number of GdE lesions at Month 12 will be analyzed using a negative binomial regression model with factors for treatment, region, age, and baseline number of GdE lesions. The key secondary endpoint of time to onset of disability progression will be compared between treatment groups using Kaplan-Meier estimation and a Cox proportional-hazards model adjusted for region, age, and baseline EDSS score. Results will be summarized by randomized treatment group and expressed as proportions, corresponding 95% confidence intervals, and p-values. Disability progressions confirmed at 3 months and at 6 months will be analyzed separately.

Other secondary endpoints that are defined as continuous variables will be analyzed using analysis of covariance models adjusted for region, age, and baseline measurements of the response parameter of interest. Other secondary endpoints defined as response proportions will be analyzed using a Cochran-Mantel-Haenszel test stratified by region and baseline EDSS category.

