# 7. DEMOGRAPHICS, MEDICAL HISTORY AND BASELINE CHARACTERISTICS

### 7.1. Demographics

The demographics and baseline characteristics will be presented in tables. The demographic characteristics consist of age, age category, sex, race, ethnicity, weight, weight category, height, body mass index, and region. A patient's age in years is calculated using the date of the informed consent and date of birth, or recorded directly on the eCRF. Age will be summarized using the descriptive statistics. The number and percentage of patients in each age category (18-19, 20-29, 30-39, 40-49, 50-55, and >55, as well as <40, ≥40), and in each race category (White, Black, Asian, American Indian or Alaska Native, Native Hawaiian or Other Pacific Islander, and Other) will be reported. The demographics and baseline characteristics summaries will be presented for both ITT and PP populations.

Demographics and baseline characteristics data will be listed.

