#### SDMT Z-score Calculation

For the SDMT, the z-score for each patient at each time-point will be created by subtracting the reference population's baseline mean score on the SDMT from the patient's SDMT score and dividing by the baseline SD on the SDMT of the reference population, i.e.

$$Z_{SDMT} = \frac{SDMT \text{ raw score} - MEAN(reference)}{SD(reference)}$$

and SDMT raw score = # of correct items within the timeframe of the test. The reference population will be the study population.

For missing post-Baseline values, if a patient is missing the SDMT score due to MS related physical limitation or other physical limitations, then a score of 0 will be assigned. If the reasons for missing score is due to other reasons (non-compliance, missed visits), then LOCF from post-Baseline values will also be used as to impute the z-score for that visit. If a value is not available to carry forward, the mean of the available z-scores using all available data from the same treatment group, will be calculated at the specified visit and used as the imputed value. Values imputed using the mean will not be carried forward to other visits.

The change from Baseline in the MSFC scores and the actual values at each visit will be summarized in each treatment group. The changes in MSFC scores at Month 24 will be analyzed and compared between treatment groups using an ANCOVA model adjusting for region, EDSS category at Baseline, and the Baseline MSFC score.

LCLA is performed with standardized set of charts (Sloan charts or Tumbling E charts) to assess low contrast visual acuity. Each chart corresponds to a different contrast level, and charts are scored according to the number of letters that are identified correctly.

Change from Baseline in visual function test scores as assessed by LCLA will be summarized by treatment group and time point, and will be compared at Month 24 between treatment groups using ANCOVA adjusted for region, EDSS category at Baseline, and the Baseline visual function test score.

### Secondary Endpoint: Change in MSQOL-54 score from Baseline to Month 24

Actual scores and change from Baseline by visit will be summarized for each of the 12 subscales, the 2 summary scores, and the 2 single-item measures shown below:

- Subscales
  - 1. Physical function
  - 2. Role limitations physical
  - 3. Role limitations emotional
  - 4 Pain
  - 5. Emotional well-being
  - 6. Energy
  - 7. Health perceptions
  - 8. Social function
  - 9. Cognitive function

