  - 10. Health distress
  - 11. Overall quality of life
  - 12. Sexual function
- Summary scores
  - 1. Physical health composite summary
  - 2. Mental health composite summary
- Single item measures
  - 1. Satisfaction with sexual function
  - 2. Change in health

Comparisons of the change from Baseline to Month 24 for the 2 summary scores only between treatment groups will be analyzed by an ANCOVA model adjusted for region, EDSS category at Baseline, and Baseline summary score of interest. Missing data will be imputed using a mixed-effects regression model (random slope and intercept).

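### Protocol and SAP give different covariates for the continuous other secondary endpoints in Part B; one model with both age and EDSS category would settle it at almost no cost

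*SAP*

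**What the plan says.** Protocol 13.6.4 (Efficacy, Part B) has one sentence for all other secondary endpoints that are continuous: "analysis of covariance models adjusted for region, age, and baseline measurements of the response parameter of interest". It has no EDSS term.

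SAP 9.3.1 sets out a model for each outcome:

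- Brain volume (change and percent change): "model adjusted for region, EDSS category at Baseline, and brain volume at Baseline".
- MSFC: "ANCOVA model adjusting for region, EDSS category at Baseline, and the Baseline MSFC score".
- LCLA: region, then "EDSS category at Baseline, and the Baseline visual function test score".
- MSQOL-54 physical and mental summary scores: region, then "EDSS category at Baseline, and Baseline summary score of interest".

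Age appears in none of the four. SAP 9.3.1 gives no reason for the change and no sensitivity analysis with the protocol's covariates. Age is available, since SAP 7.1 states: "The demographic characteristics consist of age, age category, sex".

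Protocol 13.3 describes the SAP as giving detail and expanding on the protocol. SAP 2 says that it is to be read together with the protocol. Neither says which prevails where they conflict.

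**The concern.** Two models are specified for the same Month 24 comparisons, and in general they give different estimates, confidence intervals and p-values. A reader of the final report could not tell from the documents which one was meant to be primary.

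The SAP's choice is also out of line with its own practice. Baseline age is in its models for relapse rate (9.1.1), T2 and GdE lesion counts (9.2.1) and disability progression (9.2.1). It is missing only from the ANCOVAs, whose outcomes (brain volume, walking, hand function, cognition, vision, quality of life) may plausibly vary with age across an eligible range of 18 to 55 years.

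The protocol's choice has a gap of its own. EDSS category is a randomisation stratum (Protocol 13.4, SAP 5.2), yet it is absent from the protocol's ANCOVA.

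What is at stake is some precision and clear pre-specification for a group of named secondary endpoints. The primary result is not at stake.

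**Working it through.** The documents state no power, standard deviation or effect size for these endpoints, so there is no planned figure to reproduce. The core of the check is a comparison of covariate lists.

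| Analysis | Region | Age | EDSS category | Baseline value of outcome |
|---|---|---|---|---|
| Protocol 13.6.4, continuous other secondary | yes | yes | no | yes |
| SAP 9.3.1, brain volume | yes | no | yes | yes |
| SAP 9.3.1, MSFC | yes | no | yes | yes |
| SAP 9.3.1, LCLA | yes | no | yes | yes |
| SAP 9.3.1, MSQOL-54 summaries | yes | no | yes | yes |

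The difference is the same for all four outcomes. Region and EDSS category are the strata that both documents use for the CMH tests of lesion-free proportions. The SAP may have carried those strata over to the ANCOVAs, but it does not say so.

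**Possible value of adding age to the SAP model.** Inputs are 400 patients per arm (SAP 5.1) and R², the share of residual variance that age explains beyond region, EDSS category and the baseline value. R² is assumed to be 0.02 to 0.10. The extra patients per arm that would give the same precision are 400/(1 − R²) − 400:

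- R² = 0.02: 400/0.98 − 400 = 8
- R² = 0.05: 400/0.95 − 400 = 21
- R² = 0.10: 400/0.90 − 400 = 44

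**The same on the power scale.** The test is two-sided at 0.05 with 400 per arm. Suppose a comparison has 80% power with age in the model. Without age the residual variance rises by a factor 1/(1 − r²), where r is the assumed partial correlation of age with the outcome.

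| Assumed r | Variance factor | Power without age |
|---|---|---|
| 0.1 | 1.01 | 79.6% |
| 0.2 | 1.04 | 78.4% |
| 0.3 | 1.10 | 76.2% |
| 0.4 | 1.19 | 72.8% |

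**Room for choosing between the two models.** A simulation under no treatment effect used 20,000 runs per scenario, 400 per arm and a nominal 5% level. It assumed 15% of patients with EDSS above 3.5, balanced across arms, and left region out. Correlations with the outcome were assumed at 0.1 to 0.4 for age and 0.1 to 0.3 for EDSS category. Rejection rates were:

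- Protocol covariates alone: 3.7% to 4.8%. This is conservative because a balanced stratification factor is left out of the model.
- SAP covariates alone: 4.9% to 5.2%.
- Smaller of the two p-values: 5.3% to 6.4%.

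Neither model used alone materially exceeds the nominal level. Picking the better of the two inflates it slightly.

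**The case against.** The strongest reply is that the SAP has made a reasonable exchange. EDSS category is a randomisation stratum and belongs in the model. Including it brings the ANCOVAs into line with the CMH tests, and in the simulation it removed the conservatism of the protocol model. This stands. A reader might infer that the SAP gives up precision for nothing, but the documents do not support that: the SAP drops one covariate and gains another, and nothing in them shows which is worth more.

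A reader might also take 8 to 44 patients per arm as the cost of the SAP departing from the protocol. It is not. That range compares the SAP model with a model holding both covariates, which appears in neither document, and it rests on an assumed R².

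Third, a reader might infer wide freedom to choose a model after seeing the data. Protocol 13.3 requires the SAP to be final before any database lock, and within the SAP each outcome has one model. With no rule of precedence some ambiguity remains, but the simulated inflation from exploiting it is small.

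Finally, SAP 5 applies no multiplicity adjustment to other secondary endpoints, so their p-values are nominal in any case. It also names age (40 or under against over 40) as a subgroup factor. A subgroup analysis does not replace covariate adjustment, but it does mean that age is not ignored.

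**Conclusion.** The inconsistency is certain and covers every continuous other secondary endpoint in Part B. Neither model is wrong, and each is missing a covariate that the other has. EDSS category belongs in the model because it is a randomisation stratum; age is worth including because the SAP itself adjusts for it in its relapse, lesion and disability models.

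The size of the precision gain is unknown. The figures of 8 to 44 patients per arm, and of a few points of power, hold only under the assumed strength of age and show scale only. The inflation of 5.3% to 6.4% likewise depends on assumed correlations and arises only if someone picks the smaller p-value.

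The affected endpoints are outside the controlled testing sequence, and the primary and key secondary models do not change. Severity is minor.

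**What to change.** Before unblinding, put the same ANCOVA in both documents for brain volume, MSFC, LCLA and the MSQOL-54 summary scores: treatment, region, age at Baseline (continuous), EDSS category at Baseline (≤3.5, >3.5) and the baseline value of the outcome.

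This means adding age to four SAP paragraphs and EDSS category to one protocol sentence. Relative to either current model the cost is one degree of freedom, with about 400 patients per arm. No new data are needed, since both covariates are already collected.

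If the sponsor prefers to keep the SAP model, the minimum is a sentence in the SAP saying that it supersedes Protocol 13.6.4 on this point and why, with the protocol model reported as a sensitivity analysis. That resolves the conflict but leaves age out of the main analysis.
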